***To allow for the possibility of inevaluable patients, an accrual ceiling of 65 will be used.***

### **3.2 DRUG ADMINISTRATION**

All patients will undergo up to 18-liter apheresis to remove peripheral blood monocytes for dendritic cell preparation. Cells used for subsequent dendritic cell maturation will be derived from monocytes frozen during the initial apheresis. Autologous AdHER2 dendritic cell vaccine will be manufactured under cGMP conditions by the NIH Clinical Center Department of Transfusion Medicine as outlined in [Appendix 3](#). If the mononuclear cells or plasma collected are not adequate for minimum of 5 doses of vaccine, the patient will undergo optional additional leukapheresis or plasma collection per investigator's discretion.

- Autologous AdHER2 DC vaccine preparations will be assessed for release standards (nucleated cell content and concentration, appearance, flow cytometric verification of DC validation markers, viability  $\geq 60\%$ , and product sterility and safety testing) as well as for HER2 expression (percent of cells expressing HER2/neu and the ratio of geometric mean fluorescent intensity (MFI) of HER2/neu expression to isotype control).
- For patients in both Part I and Part II of the study, autologous AdHER2 DC vaccinations will be dosed according to enrollment dose levels (5, 10, 20, or  $40 \times 10^6$  viable cells/vaccine) and administered intradermally in up to two injection sites at Weeks 0, 4, 8, 16 and 24 for a total of five vaccinations. Vaccine will be administered in the 3SE Day Hospital and patients will be monitored for immediate adverse event vaccine reactions (VS, clinical assessment) for 1 hour following their first HER2 DC vaccine dose. If no adverse reactions are observed with the first vaccination, patients will be monitored for 15 minutes for all subsequent vaccinations.
- If an adverse reaction is observed following the first vaccine, the reaction will be characterized and a determination made as to whether it is considered a dose limiting toxicity (DLT) as outlined in Section [3.1.1](#). If the adverse reaction is determined not to be a DLT, the duration of post-vaccination monitoring for subsequent vaccinations will be determined by the Principal Investigator and Lead Associate Investigator as clinically indicated depending on the severity of the initial vaccine reaction.
- All patients will be given an AdHER2 DC Vaccine Report Card (refer to [Appendix 5](#)) and instructed on how to complete it, following each AdHER2 DC vaccine dose.
- Continued injection of the same forearm is permissible for patients who have one functional forearm or a medical condition that does not allow for continued injections of both forearms.

Since this protocol involves AdHER2 DC vaccination in humans using this vector for the first time, enrollment into subsequent dose level for both Part I and Part II patients will be staggered to allow for safety monitoring as outlined in Section [3.1.2](#): dose escalation will proceed as long as 0 of 6 or 1 of 6 patients within a dose level have no evidence of toxicity and at least 3 of the 6 patients within the same dose level have reached Week 12 on study before enrollment in the next vaccine dose level can begin. If no dose limiting toxicities as defined in Section [3.1.1](#) are observed in the twelve-week window inclusive of the first three vaccinations, enrollment of additional patients may proceed as quickly as is logistically feasible as outlined above and in accordance with the dose escalation parameters outlined in Section [3.1.2](#).

### 3.3 DOSE MODIFICATION AND IMMUNIZATION STOPPING RULES

Unlike trastuzumab, the AdHER2 vaccine being given in this study targets both the extracellular (EC) and transmembrane (TM) domains of HER2. Use of trastuzumab in women with breast cancer has been shown to be associated with a small, but significant risk (about 7%) for developing cardiac dysfunction. ***Exactly how trastuzumab causes cardiac toxicity is unknown.*** The goal of vaccination with this product is to stimulate the patient's own immune system to make antibodies (and also potentially killer cells) that recognize HER2. ***It is not known whether or not antibodies made by a person's own immune system will cause cardiac dysfunction.*** In addition, if antibodies made by the immune system following AdHER2 DC vaccination were to cause cardiac toxicity or other significant clinical adverse events, it would be very challenging because the immune system cannot simply be "turned off".

***Thus, no dose modifications will be made in patients receiving AdHER2 DC vaccination.*** Subjects will cease to receive immunization if they experience dose-limiting toxicity (DLT) as outlined in Section **3.1.1**.

#### Supportive Management of Patients Experiencing DLT:

- For patients experiencing Grade 2 or greater allergic or autoimmune DLT, supportive clinical intervention will be provided until the DLT resolves to  $\leq$  Grade 1.
- For patients experiencing Grade 2 or greater cardiac DLT, supportive clinical intervention will be provided until the DLT resolves to  $\leq$  Grade 1.
  - Patients will also undergo repeat LVEF measurements at 4-week intervals until LVEF returns to baseline function. Thereafter, cardiac function will continue to be monitored according to the study schema outlined in **Figure 11** until study Week 124.
  - Patients who experience Grade 2 or greater cardiac DLT that does not resolve to  $\leq$  Grade 1 will continue to receive clinical support and be monitored according to the study schema outlined in **Figure 11**.
  - until study Week 124.
- For patients experiencing Grade 3 or greater organ (dermatologic, gastrointestinal, hepatic, pulmonary, renal/genitourinary or neurologic) DLT supportive clinical intervention will be provided until the DLT resolves to  $\leq$  Grade 1.
- For patients experiencing Grade 3 or greater anaphylaxis DLT, supportive clinical intervention will be provided until the DLT resolves to  $\leq$  Grade 2.
- For patients experiencing Grade 3 or greater local injection site reactions, supportive clinical intervention will be provided until the DLT resolves to  $\leq$  Grade 1.
- **NOTE:** Once patients have completed participation in this study, **there is no provision for long term medical care** by the Clinical Center, NIH or the NCI.

### 3.4 STUDY CALENDAR

Study Procedures	Screen	Wk 0	Wk 4	Wk 8	Wk 12	Wk 16	Wk 20	Wk 24	Wk 28	Wk 32	Wk 36	Wk 40	Wk 48 	Wk 60 	Wk 76 	Wk 100 	Wk 124 
NIH Advanced Directives 	✓																
Informed Consent	✓																
Height/Wt/NYHA	✓																
Screening labs/HLA 	✓																
Physical Exam/ECOG 	✓	✓	✓	✓	✓	✓	✓	✓	✓	✓	✓	✓	✓	✓	✓	✓	✓
Concomitant Medications	✓	✓	✓	✓	✓	✓	✓	✓	✓	✓	✓	✓	✓	✓	✓	✓	✓
Clinical labs 	✓	✓	✓	✓	✓	✓	✓	✓	✓	✓	✓	✓	✓	✓	✓	✓	✓
Tumor Markers 	✓	✓	✓	✓	✓	✓	✓	✓	✓	✓	✓	✓	✓	✓	✓	✓	✓
LDH/CK/Troponin 	✓	✓	✓	✓	✓	✓	✓	✓	✓	✓	✓	✓					
TSH/25-OH Vit D	✓	✓							✓					✓			
Lymphocyte Subsets/ Ig QA/IgE	✓	✓	✓	✓	✓	✓	✓	✓	✓	✓	✓	✓	✓	✓	✓	✓	✓
Serum beta HCG 	✓	✓	✓	✓	✓	✓	✓	✓	✓	✓	✓	✓					
Urinalysis	✓	✓							✓					✓			
Anti-HER2 Ab/ Profile 		✓		✓		✓		✓		✓		✓	✓	✓	✓	✓	✓
Anti-Ad5 Antibody 		✓		✓		✓		✓		✓		✓	✓	✓	✓	✓	✓
Cellular HER2 Response 		✓		✓		✓		✓		✓		✓	✓	✓	✓	✓	✓
Immune Subset/CTCs 		✓		✓		✓		✓		✓		✓	✓	✓	✓	✓	✓
Hitachi mRNA		✓															
MRI Brain  , CT Neck  , bone scan 	✓			✓		✓		✓		✓		✓	✓	✓	✓	✓	✓
CT Chest/Abd/Pelvis 	✓			✓		✓		✓		✓		✓	✓	✓	✓	✓	✓
2-D ECHO 	✓		✓		✓		✓		✓		✓	✓	✓	✓	✓	✓	✓
AdHER2 DC vaccine 	Apheresis	✓	✓	✓		✓		✓		✓							
Vaccine Report Card		✓	✓	✓		✓		✓		✓							
Adverse Events		✓	✓	✓	✓	✓	✓	✓	✓	✓							

 As indicated in Section 12.3, all subjects  $\geq$  age 18 will be offered the opportunity to complete an NIH advanced directives form. This should be done preferably at baseline but can be done at any time during the study as long as the capacity to do so is retained. The completion of the form is strongly recommended, but is not required

 Screening labs: CBC diff, PT/PTT, acute care panel, hepatic panel, serum beta HCG, urinalysis, and the following DTM labs: Anti-HIV 1/2 Ab, Anti-HCV Ab, HBsAg, Anti-HBs Ab, anti-HTLV 1/2 Ab (pending result is acceptable for eligibility), anti-CMV IgG/IgM, and RPR. If DTM labs are performed  $>$  30 days prior to apheresis, DTM labs must be repeated. HLA will not determine eligibility and if it was done previously at the NIH it does not need to be repeated.

 Patients should be evaluated within 7 days prior to upcoming vaccination as a clearance for treatment.

 Clinical labs CBC with differential, PT/PTT, acute care panel, hepatic panel, mineral panel, total protein, amylase/lipase, uric acid, lipid panel.

 Tumor markers are optional and will be tested dependent on the primary sites. Patients with primary breast, ovarian and GI tract cancer might be tested for CA 125, CA 15-3, CA19-9, CA 27-29, and CEA. Other organ specific tumor markers can be tested

 Only until 12 weeks after the last dose of vaccination.

 Research bloods will not be used in data analysis if the patient has started on any treatment that can affect the data of the study. Week 40 and after samples will only be collected if the patient has not progressed (PD).

 This is optional and to be performed if clinically indicated. If the patient received scans within 30 days of enrollment at an outside institution the patient will not be required to have a second scan performed. Instead, the baseline scan will be used to collect target lesions.

 If the patient received scans within 30 days of enrollment at an outside institution the patient will not be required a screening scan to consent. Instead, the baseline scan will be used to identify target lesions. If the patient has bone metastasis and clinically indicated, a bone scan will be done at restaging.

 If the patient received scans within 30 days of enrollment at an outside institution the patient will not be required to have a second scan performed. Instead, the baseline scan will be used to collect target lesions. If a confirmatory scan is performed in less than 8 weeks from prior CT, the interval of CT follow-up will be adjusted to maintain 8 weeks interval to avoid unnecessary radiation exposure. For bladder cancer adjuvant indication, CT scans every 12 weeks during first 12 month, every 16 weeks for the next 12 months and at the end of study if no recurrence.

 Optional documentation on cardiac function will be collected once a patient is on study but off treatment for the purposes of long-term assessment of the impact of AdHER2 vaccination on cardiac function. Note: if the patient had an echo within 30 days of enrollment at an outside institution the patient will not be required a screening echo to consent. Instead, the baseline echo will be performed at NIH prior to treatment and used to identify target lesions.

 Dose can be delayed up to 8 weeks. The study will reset at the time of study resumption. For example, if dose at week 8 is delayed and resumed at original week 11, that week 11 will now be considered week 8.

 If there is a need for confirmatory scans based on the result of Week 48 evaluation, additional visit will occur at week 52 which will include clinical assessment with physical exam and laboratory assessment.

 Patients who progress do not require a full evaluation. Only physical exam, clinical labs, echocardiogram and AE reports will be required.

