## **1 INTRODUCTION**

### **1.1 STUDY OBJECTIVES**

#### **1.1.1 Primary Objective**

- To determine the safety and toxicity of autologous AdHER2/neu dendritic cell vaccination. Specifically, to:
  - Determine if the fraction of patients with cancer therapeutics-related cardiac dysfunction (CTRCD), (if it occurs) is sufficiently low to warrant further development in subsequent trials. CTRCD is defined as a decrease in LVEF  $\geq 10$  percentage points, to a value  $\geq 53\%$  (normal reference value for two-dimensional (2-D) echocardiography).
- To determine the immunogenicity of autologous AdHER2 dendritic cell vaccination as measured by a 3-fold increase in anti-HER2/neu antibody concentration (measured as mcg/mL) or a 4-fold increase in antibody dilution titers over baseline.

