## **11 STATISTICAL CONSIDERATIONS**

The primary objectives of this open label, single site, non-randomized, two-part, phase I study of AdHER2 DC vaccination are to determine if the fraction of patients with cardiac toxicity (if it occurs) is sufficiently low to warrant further exploration in subsequent trials and to determine an approximate estimate of the vaccine immunogenicity, as represented by the fraction of patients who develop at least a 3-fold increase in anti-HER2/neu antibody concentration (measured as mcg/mL) or a 4-fold increase in antibody dilution titers over baseline at the time points measured. An important secondary objective is to obtain a preliminary estimate of the proportion of patients who may experience tumor shrinkage or stabilization that is sufficient by modified immune response related criteria (modified irRC) to be considered stable disease, a partial response or better.

It has been reported that up to 7% of patients with HER2/neu expressing tumors treated with trastuzumab monotherapy for metastatic breast cancer developed clinically significant cardiac dysfunction including congestive heart failure. It would be considered acceptable if the therapeutic AdHER2 DC vaccine proposed for this study would produce no greater than that level of cardiac toxicity, but not acceptable if it were to be exceeded. In order to evaluate this using a limited number of patients, a two-part design, but incorporating an early stopping rule, will be implemented.

Statistical considerations pertaining to each part of the study are as follows:

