Since 0 of 20 patients already have been documented to have NO cardiac toxicity, and 0 to 2 patients out of 30 would have been acceptable per the original study design, a statistical estimate was performed to determine what the probability of having 0 to 2 of the next 10 patients in the Part 1 Expansion Cohort having cardiac toxicity would be. If the probability of cardiac toxicity were 2%, there would be 99.91% probability of 0 to 2 of 10 with toxicity; if it were 5%, there would be 98.8% probability; and if it were 10%, there would be 93% probability of 0 to 2 of 10 with toxicity. Thus, assuming the next 10 patients would have the same underlying per-patient probability of developing cardiac toxicity as the first 20 had, and it is likely to truly be at or below 10%, there is between a 93% and 99.9% probability that the next 10 patients enrolled in the Part I Expansion Cohort would have 0 – 2 toxicities and therefore 0 – 2 of 30 would have cardiac toxicity as per the original study design. Consequently, FDA approval was received on 12/14/15 to initiate enrollment in Part II of the study in parallel, while enrollment of the Part I Expansion Cohort is completed.

The fraction of subjects with immunogenicity, defined as a 3-fold increase in anti-HER2/neu antibody concentration (measured as mcg/mL) or a 4-fold increase in antibody dilution titers over baseline will be reported, along with 80% and 95% confidence intervals, at the following time points: Weeks 4 (after 1 vaccine dose), 8 (after 2 vaccine doses), 12 (after 3 vaccine doses), 28 (after 5 vaccine doses), 48 and 52 weeks and during extended follow-up for monitoring of cardiac adverse events at weeks 76, 100 and 124.

Finally, as a secondary objective, the fraction of subjects who have stable disease, an objective partial response or better by modified irRC will be determined along with appropriate confidence intervals with exceptions to the PR assessment at Week 12 as noted in Sections [3.5.1](#), [3.5.2](#) and [6.2.4](#). The fraction identified in this trial will potentially be useful information for design of any subsequent trials using this vaccine in both of the patient populations being studied.

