### **Quantitative Anti-HER2 Antibody Testing: Weeks 0, 8, 16, 24, 32, 40, 48, 60, 76, 100, and 124**

**Purpose:** To determine the immunogenicity of autologous Ad HER2 dendritic cell vaccination as measured by a 3-fold increase in anti-HER2/neu antibody concentration (measured as mcg/mL) or a 4-fold increase in antibody dilution titers over baseline.

**Specimen Processing:** 1 10mL Red Top Clot activator

Specimens will be processed by the Clinical Support Laboratory Leidos Biomedical Research, Inc. Serum will be aliquoted into vials and cryopreserved until ready for interrogation in batched specimen assays.

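### After the fifth dose, every reported immunogenicity fraction with a scheduled antibody draw comes from patients selected for not having progressed, and no denominator is stated

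*Combined protocol and SAP*

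**What the plan says.** - **Objective.** Section 1.1.1 lists as primary: "To determine the immunogenicity of autologous AdHER2 dendritic cell vaccination as measured by a 3-fold increase in anti-HER2/neu antibody concentration", or a 4-fold rise in titer. The opening of Section 11 repeats this as the fraction of patients who develop the concentration rise "or a 4-fold increase in antibody dilution titers over baseline at the time points measured".
- **Reporting.** Section 11.3 gives the fraction with 80% and 95% confidence intervals at Weeks 4, 8, 12 and 28, then "48 and 52 weeks and during extended follow-up for monitoring of cardiac adverse events at weeks 76, 100 and 124".
- **Draws.** The calendar in Section 3.4 and Appendix 6 schedule quantitative antibody testing at "Weeks 0, 8, 16, 24, 32, 40, 48, 60, 76, 100, and 124".
- **Restrictions.** Footnotes 8-11 to the calendar say "Week 40 and after samples will only be collected if the patient has not progressed (PD"), and also "Research bloods will not be used in data analysis if the patient has started on any treatment that can affect the data of the study". Footnote 18, covering Weeks 60 to 124, agrees: "Patients who progress do not require a full evaluation". It leaves only examination, clinical labs, echocardiogram and adverse event reports.
- **Dosing and use.** Section 3.1 places the fifth and last dose at Week 24. Section 3.1.2 says that, if no dose-limiting toxicity is seen, immunogenicity fractions and clinical outcomes by dose level will identify the biologically optimal dose.

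Sections 11 and 11.3 state no denominator, no rule for missing antibody samples, and no condition that the late fractions apply only to progression-free patients.

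**The concern.** A fraction of subjects with an antibody response is naturally read as a property of the vaccinated population. From Week 40 the disease course decides who contributes a sample, so the late fractions describe a different group or depend on how the unsampled are scored. Part of any change between Week 8 and Week 48 could then reflect who remains rather than what the vaccine does. The same fractions feed the choice of dose for later studies. If doses differ in how many patients stay progression-free, for whatever reason, the late fractions are not comparable between them.

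**Working it through.** The plan states no sample size, precision or expected rate for immunogenicity, so there is no figure of its own to reproduce on this point.

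**Step 1. Match reporting weeks to draws.**

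- Reporting weeks (Section 11.3): 4, 8, 12, 28, 48, 52, 76, 100, 124.
- Post-baseline draws (Section 3.4, Appendix 6): 8, 16, 24, 32, 40, 48, 60, 76, 100, 124.
- On both lists: 8, 48, 76, 100, 124.
- Of these five, four (48, 76, 100, 124) fall under the Week 40 restriction. Week 8 does not, but Section 11.3 itself labels it as following two doses.
- Weeks 4, 12, 28 and 52 have no scheduled antibody draw. Section 5.1 implies a conditional evaluation at Week 52 when a confirmatory scan is needed, but that too lies after Week 40.

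The first reporting week with a scheduled draw after the fifth dose is therefore Week 48, and it is restricted.

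**Step 2. What a late fraction estimates.** Let s be the share progression-free at Week 48, a the response rate in those patients, and b the rate in progressors. The documents give none of these; the values below are assumptions.

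- Over those sampled: a
- True rate in all vaccinated: s·a + (1−s)·b
- Over all treated, unsampled counted as non-responders: s·a

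| s | a | b | Over sampled | True, all vaccinated | Over all treated |
|---|---|---|---|---|---|
| 20% | 40% | 40% | 40% | 40% | 0.2×0.4 = 8% |
| 50% | 40% | 40% | 40% | 40% | 0.5×0.4 = 20% |
| 20% | 60% | 20% | 60% | 0.12+0.16 = 28% | 12% |
| 50% | 60% | 20% | 60% | 0.30+0.10 = 40% | 30% |

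The sampled-only fraction equals the true rate only when a = b. The all-treated fraction is too low whenever any unsampled progressor is a responder.

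The denominator also drives the interval. With 30 patients in a part (the target in Section 3.1.2), s = 20% and 4 responders among the 6 sampled, the exact 95% interval is 22% to 96% for 4/6 and 4% to 31% for 4/30.

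**Step 3. Unequal opportunity, if response is counted at any time.** A patient who never progresses has 10 post-baseline draws. One who progressed before Week 40 has 4 (Weeks 8, 16, 24, 32). With probability q per draw of crossing the threshold without a true response (assumed, draws independent), the chance of at least one crossing in k draws is 1 − (1−q)^k.

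| q | 4 draws | 10 draws |
|---|---|---|
| 1% | 1 − 0.99^4 = 4% | 1 − 0.99^10 = 10% |
| 3% | 1 − 0.97^4 = 11.5% | 1 − 0.97^10 = 26% |
| 5% | 1 − 0.95^4 = 18.5% | 1 − 0.95^10 = 40% |

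**The case against.** **Reporting is week by week.** Section 11.3 lists time points, and the phrase in Section 11 can be read the same way. A single-week fraction gives each patient one chance, so Step 3 does not apply to it. This stands: the unequal-opportunity problem is conditional on an any-time definition, which Section 11 permits but does not require. The selection in Step 2 applies to single-week fractions regardless.

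**The bias may be nil.** If response is unrelated to progression, the sampled-only fraction is unbiased. That is correct, and nothing in the documents fixes the direction or size. But the plan neither chooses that denominator nor states that assumption.

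**Unrestricted draws exist, and late weeks are secondary in purpose.** The Précis sets 48 weeks for primary endpoints, later follow-up is described as cardiac monitoring, and Section 11 seeks only an approximate estimate. Draws at Weeks 16, 24 and 32 are not limited by progression. True, but Section 11.3 reports none of those three weeks, and Week 48 is restricted even within the primary period.

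**Progression must be confirmed.** Section 6.2.7 requires a second observation at least 4 weeks later, and Section 3.5.1 lets some progressors stay on therapy. This can delay the cutoff but gives no exception to it.

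**Stronger readings that the documents do not support:**

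- A reader might set 10 draws against 1 for an early progressor. The single draw needs a switch of therapy at once after Week 8. It comes from the separate rule on other treatment, which has an evident purpose: Section 1.2.9 describes special assays used to avoid trastuzumab interference. The Week 40 rule alone gives 10 against 4.
- A reader might conclude that an association between antibody response and clinical benefit is built into the analysis. Section 1.1.2 names no comparison of antibody responders with non-responders, and Section 3.1.2 compares dose levels. No within-patient analysis of this kind is specified.

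**Conclusion.** The concern holds for the late fractions. Followed as written, Section 11.3 reports no immunogenicity fraction with a scheduled draw after the full five-dose course that covers the vaccinated population. Four of the five reporting weeks with a scheduled draw are restricted to patients who have not progressed, and the fifth follows only two doses.

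If all treated patients form the denominator, the fraction is understated. With equal 40% response, it reads 8% at 20% progression-free and 20% at 50%. If those sampled form the denominator, it is a rate in progression-free patients, and its distance from the all-patient rate cannot be known from the documents. All these magnitudes rest on assumed shares, response rates and assay error.

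No stated figure in the plan is contradicted, and immunogenicity carries no test or go/no-go threshold. The consequence is a primary estimate that does not describe its intended population and may inform the dose choice, although better-placed draws are already scheduled.

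**What to change.** In Section 11.3:

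1. Base the primary immunogenicity fraction on Weeks 8, 16, 24 and 32, reported by week, over vaccinated patients with a Week 0 sample. Name Week 32 as the reading after the full course.
2. At each week show the numbers vaccinated, sampled and excluded for other treatment, and state how a missing or excluded draw is scored.
3. Report Weeks 40 to 124 separately, labelled as durability among patients who are progression-free and have not started other treatment.
4. If an any-time responder is reported, restrict it to Weeks 8 to 32 and show the number of samples per patient.
5. If antibody status is ever compared with clinical outcome, fix antibody status at a landmark week and count only later outcomes.
6. Align the reporting weeks with the draw schedule, since Weeks 4, 12, 28 and 52 have no scheduled draw.

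The cost is an amendment to the analysis text, with no added blood draws. It does change the weeks on which a primary measure rests, so it should be settled before the antibody data are analysed. Two drawbacks remain. A first rise after Week 32 appears only in the durability table. Samples through Week 32 can still be lost to a switch of therapy, which is why the counts in item 2 matter.
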